- Scholarly and journalistic activities (e.g. biography, literary criticism, legal research, and historical scholarship);
- Public health surveillance activities for the purposes of identifying, monitoring, assessing, or investigating potential public health signals, onsets of disease outbreaks or conditions of public health importance; or
- The collection and analysis of information, biospecimens or records by or for a criminal justice agency for activities authorized by law or court order for criminal justice or criminal investigative purposes

If your project solely involves one or more of the three bullet items above, check "no" to the answer to Question 1 below:

* 1. Does your project involve a systematic investigation and is intended to develop or contribute to *generalizable knowledge* (e.g. publication, presentation at a conference, or thesis)?
 Yes No

* 2. Does your research involve obtaining data from or about living individuals through interaction with them, or through an intervention?
 Yes No

Identifiable Information

* 3. Will any study team member receive, possess, or have access to any of the following identifiers listed below
 Yes No

- Name
- Geographic subdivision smaller than a state unless according to currently publicly available data from the Census Bureau the geographic unit formed consents more than 20,000 people.
- Telephone Numbers
- E-Mail addresses
- Social Security Numbers
- Medical Record Numbers
- Health Plan Beneficiary numbers
- Account Numbers
- All elements of date (except for year) directly related to an individual (e.g. birth date, admission date, discharge date, date of death), all ages over 89, and elements of dates (including year) indicative of age, except such as ages and elements may be aggregated into a single category of age 90 or older
- Certificate / license number
- Vehicle identifiers (e.g. serial number, VIN, license plate number)
- Device identifiers & serial numbers
- Biometric Identifiers including voice and fingerprints
- Full face photographic images and any comparable images
- Video and voice recordings
- Any other unique identifying number, characteristic or code
- Access to the key to the code allowing you to link the data to the identity of study participants

HRPP Questionnaire Cont...

* 4. Is your project a clinical trial?
NIH defines a clinical trial as: "A research study in which one or more human subjects are prospectively assigned to one or more interventions (which may include placebo or other control) to evaluate the effects of those interventions on health-related biomedical or behavioral outcomes." Interventions include drugs, medical devices, procedures, vaccines, as well as noninvasive approaches such as surveys, education, and interviews.
 Yes No

5. Cancer Related Research

* Does your study involve cancer patients under current treatment or with evidence of current disease; target cancer survivors, or participants which may be at high risk for cancer?
 Yes No

* Does your study involve participants from a healthy population but are at a high risk for cancer or is cancer a study outcome?
 Yes No

IDENTIFIERS

Select any PHI identifiers you will be accessing (i.e., using), recording (i.e. collecting), or disclosing (i.e. sharing outside of SDSU) among the following:

* Use the "+" symbol to add additional rows and select applicable PHI Identifiers

* PHI Identifier	Accessing	Recording	Disclosing
Names			
Telephone numbers			
E-mail addresses			
Any other unique identifying number, characteristic, or code			
Access to the key to the code allowing you to link the data			

BASIC STUDY INFORMATION

Investigator(s) Experience

* List relevant experience of all study team members as it pertains to this research.

Semantic knowledge, or knowledge of a word's meaning, has strong ties to reading comprehension and long-term academic outcomes, particularly in the school years. Children with developmental language disorder (DLD), language impairment in the absence of any causal factors, often show deficits in semantic knowledge and acquisition. It is generally accepted that these deficits are driven by difficulty with the process of adding meaning to a new word with repeated exposures to the word, or configuration. What is unknown is what underlies deficits in configuration and whether these deficits vary across the DLD profile. The goal of this project is to elucidate the semantic learning deficits in DLD. Toward this goal, this project uses a combined electroencephalogram (EEG) - behavioral methods approach to examine the cognitive and linguistic processes engaged during semantic learning in school-age children with and without DLD. The inclusion of EEG will allow for a real-time examination of semantic learning and associated cognitive and linguistic processes. 10-12 year old children with and without DLD will complete a behavioral assessment battery and semantic learning task while their EEG is collected. Behavioral data will be analyzed for semantic learning group differences (Aim 1) and the types of errors that children make when they are unable to retrieve a correct meaning (Aim 2). EEG data will be analyzed in two ways. The event-related potential (ERP) analysis will examine changes in semantic processing, indexed by the N400, during learning (Aim 1). Time frequency analysis of the EEG will examine the engagement of neural processes associated with lexical retrieval (theta) and attention/inhibition (alpha) during learning (Aim 1). Behavioral and EEG methods will be combined to examine individual differences related to semantic learning outcomes and fine-grained differences in N400 learning effects across groups (Aim 2). Taken together, findings will inform our understanding of the nature of the semantic learning deficits in school-aged children with DLD. This understanding is prerequisite for targeted intervention that would help these children learn how to learn.

* Please provide a list of references to support the information found in the background and significance section.

10-12 year old children, both those with typical language development and those with DLD, will serve as participants for this research. DLD is defined as impairment with language and no other deficit (e.g. neurological impairment, intellectual deficit, ADHD, autism, etc.) affecting language abilities.

* 4. Planned analyses:

Data analyzed will include behavioral performance on a semantic learning task (percent correct and analysis of incorrect responses) and EEG data time-locked to the novel word being learned. To compare behavioral semantic learning performance, behavioral data will be subjected to a one-way ANOVA to evaluate a possible effect of group (DLD, TL) on accuracy and the error analysis. To evaluate changes in brain processing of the novel word during

learning and potential group differences in neural processing. a 2 group (DLD, TL) x 3 presentation (1st sentence, 2nd sentence, 3rd sentence in the set) ANOVA will be run on the EEG data.

* 5. Potential benefits:

There are no direct benefits to the participants. Researchers will learn more about the nature of the semantic learning deficits in children with DLD.

* 6. Potential risks:

Participants will be exposed to very minimal risks. Due to the length of the assessments and semantic learning task, participants may experience some boredom and stress, which will not exceed the levels they experience in everyday life and breaks will be provided to alleviate any fatigue or boredom participants may experience. The EEG cap may be a little stressful for some participants and may seem itchy or uncomfortable. The risks and inconveniences associated with the assessments are reasonable in relation to the anticipated benefits discussed above.

* 7. Risk management procedures:

Participants will be informed about the procedure and the minimal risk. If at any time the participant does not feel comfortable with the EEG process, the experiment will be terminated. To help alleviate fatigue or boredom, breaks will be provided throughout the assessment session. To maintain confidentiality, a code number will replace participants' names on all of the information collected from them. All data will be marked with a participant code number only. Research records will be kept confidential to the extent allowed by law and stored in a locked filing cabinet at the Language Learning Lab and only personnel associated with this research will have access.

Research Design and Methods

* Specify aims of the research that include the hypotheses to be tested, research questions to answer, data to be gathered and tested.

The central hypothesis of this research is that children with DLD engage cognitive and linguistic processes at different points during configuration compared to their typical peers, resulting in poorer semantic learning outcomes. Aim 1. To investigate the cognitive and linguistic processes underlying configuration in children with DLD and typical language (TL) peers. Aim 2. To investigate individual differences in configuration in children with DLD and TL peers. Toward these aims, we will administer a series of behavioral assessments to establish language status and a semantic learning task, during which we will collect EEG. See below for details.

* Use this space to provide a detailed list of every step you will take to test your hypothesis. Beginning with recruitment strategy, data collection , to analysis of research results.

Participant Recruitment: The PI has experience recruiting children with DLD and has established relationships with community agencies and professionals who work with these children, including local speech-language clinics, school districts, and literacy centers. Participants, both DLD and TL, will be recruited from these and other locations/professionals by way of flyers and in-person recruitment, when possible. General procedures: All participants will be screened over the phone or via email for language history, handedness, medication use and history of neurological disorders or dysfunction. Upon arriving at the lab, participants will complete a behavioral test battery including nonverbal cognition, receptive and expressive vocabulary, general language and verbal working memory measures. For the EEG task, an electrode cap, similar to a lycra swimcap, will be placed on the participant's head. The EEG caps used in the PI's lab are designed for research conducted with infants, children, adolescents, and adults. The EEG cap is being used as described for use with children according to the instructions for use document provided by the manufacturer. The researcher will apply a small amount of saline solution to each electrode (total: 64 on the scalp, another two above and below the left eye). The solution enables the small sponge in each electrode to expand and make contact with the scalp. When this contact is made, the measured impedance (measurement of resistance) decreases, and the impedance values can be observed on a computer monitor visible to the researcher. When the impedance level is decreased on most electrodes, the experiment can begin. Participants will be seated in an electrically-shielded room in the Language Learning Lab. The electrode cap will collect electrical activity from the brain as participants complete the semantic learning task, as described below. Participants will silently listen to naturally-paced sentences presented in sets of 3 sentences. The last word of each sentence will be a nonsense word. After each set of 3, the participant will be asked to provide the meaning of the nonsense word, if possible. An experimenter, sitting in the room but out of sight of the participant so as not to distract them, will write down the word provided by the participant. The participant will be asked to sit as still as possible while the stimuli are being presented, with the exception of when they are asked to define the nonsense word. Participants will be given breaks as needed. Following completion of the semantic learning task, participants will complete a word recognition task where they hear 200 nonsense words one at a time and push a button to indicate whether they've heard it before or not. Data analyzed will include behavioral performance on the semantic learning task (percent correct and incorrect responses for error analysis) and EEG data time-locked to the nonsense word in each sentence. To compare behavioral semantic learning performance and errors, behavioral data will be subjected to a one-way ANOVA to evaluate a possible effect of group (TL, DLD). To evaluate changes in brain processing of the novel word during learning and potential group differences in neural processing, a 2 group (TL, DLD) x 3 presentation (1st sentence, 2nd sentence, 3rd sentence in the set) ANOVA will be run on the EEG data.

PARTICIPANT INFORMATION

Study Population

Instructions: Enter the total number of adults and children you wish to recruit for your study. If you plan on recruiting members of a vulnerable population, indicate using the check boxes below and enter the total number expected for that category.

ADULTS (18+)

- Cognitively Impaired
- Prisoners
- Pregnant Women
- Other

Children

- Cognitively Impaired
- Prisoner/Detainee
- Pregnant Women

Other

* Population:
language impaired

TOTAL:

* Describe how the number of subjects was determined (e.g. statistical significance).

A priori power analyses were conducted with G*Power using preliminary data to determine sample sizes needed for the proposed project. For the behavioral data, the semantic learning accuracy analysis requires 16 participants/group for power=0.95, f=0.6, α =0.05, the error analysis requires 14 participants/group for power=0.95, f=0.6, α =0.05, and the regression requires 24 participants/group for power=0.95, f²=0.35 α =0.05. The ERP analysis requires 18 participants/group for power=0.95, f=0.6, α =0.05. The time frequency analysis requires 12 participants/group for power=0.95, f=0.6, α =0.05. This is consistent with evidence that time frequency analysis is more robust to noise than ERP requiring fewer trials and participants. Therefore, a targeted sample of 25 participants/group should easily provide at least power=0.8 for all proposed variables.

* List the criteria for inclusion and exclusion of subjects in this study.

Participant exclusion criteria include: neurological disorders (i.e., ASD, ADHD), significant neurological history (i.e., head injury, epilepsy), left handedness, medication other than over-the-counter allergy medications, and/or nonverbal IQ less than 70, as measured by the Wechsler Intelligence Scale for Children. Performance on a standardized language omnibus assessment (Clinical Evaluation of Language Fundamentals-5 Core Language Scale; CELF) will be used to classify children as DLD if they earn a standard score of < 80, else they will be classified as TL. The use of a standard score of 80 on the CELF as a cut point for identification of DLD is supported by good sensitivity (0.97) and specificity (0.97). The use of this validated cut score is the best assurance that children will be correctly identified for their respective groups. DLD and TL groups will be equivalent on age, nonverbal cognition, handedness, and gender, as measured by parental responses to a questionnaire administered during participant intake.

If applicable, provide a rationale to support subject exclusion for populations who might benefit from participation in the research.

This age range was selected, in part, because the rate of vocabulary growth in children with DLD further decreases relative to TL peers around age 10.

Subject Recruitment

How will you contact potential subjects for recruitment?

- Record Review
- In-Person
- Classroom
- Flyer
- Third Party Referral
- Paid Advertisements
- Telephone
- Email
- Letter
- Electronic Participant Pool Recruitment
- Other

Please upload a copy of any recruitment language that will be used to introduce this study to potential participants.

Subject Screening

What instrument(s) will you use to determine subject eligibility?

- Survey/Screening/Checklist
- Phone Screen
- Health Records
- Other
- N/A

Survey/Screening/Checklist Detail

- Mail
- In-Person
- Online
- Other
- SONA

* Are you going to obtain informed consent prior to participant screening?

Yes No

* Explain how consent will be obtained prior to screening.

Consent will be obtained via phone or email, per parent request, following a script which has been uploaded.

Please upload instrument

Phone Screen Detail

* Are you going to obtain documentation of informed consent prior to participant screening?

Yes No

* Explain how documented consent will be obtained prior to screening?

Consent will be obtained via phone or email, per parent request, following a script which has been uploaded.

Please upload phone screen or phone script

Subject Involvement Expectations

* Describe the tasks in the order that the subject will be asked to complete them. If tasks vary by group, please indicate the group in the description.

Name of Task	Brief Description	Time to Complete
Visit 1	Demographic questionnaire, Edinburgh Handedness Inventory, Wechsler Intelligence Scale for Children, Clinical Evaluation of Language Fundamentals, Nonword Recognition Task, Flanker Inhibitory Control and Attention task	0-5 hours
Visit 2	EEG cap application, semantic learning task, word recognition task	0-5 hours

Research Interviews/Surveys/Questionnaires/Focus Groups

* List all measures used for this study and provide rationale for its use. Indicate if the measure is validated or published:

Measure	Availability	Validation
Demographic questionnaire	Privately Available	PI Developed
Edinburgh Handedness Inventory	Publicly Available	Peer Approved
Wechsler Intelligence Scale for Children	Publicly Available	Peer Approved
Clinical Evaluation of Language Fundamentals	Publicly Available	Peer Approved
Nonword Repetition Task	Publicly Available	Peer Approved
Flanker inhibitory control and attention	Publicly Available	Peer Approved
Semantic learning task	Privately Available	PI Developed
Word recognition task	Privately Available	PI Developed

Please upload measures

Research Setting

* Identify the location and describe the setting, include any safety/privacy concerns to study participants. The study will be conducted at [name] Learning Lab ([name]). This laboratory is equipped to administer behavioral measures and collect and record EEG data. The laboratory is typically locked and only accessible to laboratory personnel.

* Will the researcher(s) be traveling to another country to conduct the research?

Yes No

Payment/Incentives to Participants

What form of payment/incentive will be provided?

Payment/Incentives to Participants Details

(Check all that apply):

 Reimbursement	 Compensation
 Drawing	 Small Gift
 Cash/Check	 Gift Card
 Other	 None

* Describe each type of payment/incentive checked above.

Participants will be reimbursed with cash at a rate of \$15/hour of participation

If applicable, please provide a schedule for any prorated payments or incentives.

The prorated rate is \$15/hour of participation, even if participation isn't completed.

CONSENT PROCESS AND PROCEDURES

Informed Consent

How will you obtain informed consent? (Click [HERE](#) for Informed Consent Templates and Guidance)

Please Select

 Comprehensive written	 Request for alteration or waiver of informed consent requirement
 Short form	 Request for waiver of documentation (Signature not Required)
 Comprehensive oral	 Pre-existing consents(s) covers this activity
 Legally authorized representative consent	 Broad Consent

Minors and Cognitively Impaired Persons Detail

(Check all that apply)

 Documentation of Assent	 Request for waiver or alteration of informed consent/parental permission/legally authorized representative consent
 Request for waiver of documentation of assent	 Parental permission or other Legally Authorized Representative in addition to assent
 Request for waiver or alteration of assent	

* Will your assent be translated into a foreign language?

Yes No

* If the child attains the age of majority during study participation, how will you obtain consent?

N/A

RISK/BENEFIT/DATA MANAGEMENT

Potential Benefits

Are potential benefits specific to the participant (check all that apply)

- Indirect
- Direct
- N/A

Are potential benefits specific to society (check all that apply)

- Indirect
- Direct

* Describe benefits indicated above.

There are little to no direct benefits to participants. Participation in this study will advance knowledge about brain representations of semantic learning, particularly differences between TD children and children with DLD. Information gained from this study will inform theories of DLD and potential techniques for semantic learning intervention with these children.

Risk Assessment and Data Storage Safety Measures/ Risk Management

* Select the level of risk:

Minimal Risk

- Minimal Risk: That the probability and magnitude of harm or discomfort anticipated in the research are not greater in and of themselves than those ordinarily encountered in daily life or during the performance of routine physical or psychological examinations or tests.
- Greater than Minimal Risk: That the probability and magnitude of harm or discomfort anticipated in the research are greater in and of themselves than those ordinarily encountered in daily life or during the performance of routine physical or psychological examinations or tests.

* Describe risks other than loss of privacy and breach of confidentiality associated with the minimal or greater than minimal risk research, as indicated above.

Participants will be exposed to very minimal risks. Due to the length of the assessments and semantic learning task, participants may experience some boredom and stress, which will not exceed the levels they experience in everyday life and breaks will be provided to alleviate any fatigue or boredom participants may experience. The EEG cap may be a little stressful for some participants and may seem itchy or uncomfortable. The risks and inconveniences associated with the assessments are reasonable in relation to the anticipated benefits discussed above.

* What procedures are researchers using to protect personal identifiers and human subject research data, remember use of passwords, encryption of data stored, and who will have permission to access the data? Participants will be informed about the procedure and the minimal risk. If at any time the participant does not feel comfortable with the EEG process, the experiment will be terminated. To help alleviate fatigue or boredom, breaks will be provided throughout the assessment session. To maintain confidentiality, a code number will replace participants' names on all of the information collected from them. All data will be marked with a participant code number only. Research records will be kept confidential to the extent allowed by law and stored in a locked filing cabinet at the Language Learning Lab and only personnel associated with this research will have access.

Data Safety Monitoring Plan (DSMP)

* Will any of the data be released outside of the research study team? (other than to publisher)

- Yes
- No

* Please explain:

For the purpose of replication, deidentified data may be provided upon request to collaborators and other investigators.

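### The 14 and 16 children per group stated for the error and accuracy analyses do not fit the one-way ANOVA planned for both (it needs 20), and the error score to be tested is not defined

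*Combined protocol and SAP*

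**What the plan says.** The background text puts error types under the second aim: the behavioral data are to show "the types of errors that children make when they are unable to retrieve a correct meaning (Aim 2").

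Two places give the analysis. In the Study Abstract, item 4 (Planned analyses), the data are "percent correct and analysis of incorrect responses" and "behavioral data will be subjected to a one-way ANOVA to evaluate a possible effect of group (DLD, TL) on accuracy and the error analysis". In Research Design and Methods, the step-by-step account has "percent correct and incorrect responses for error analysis" and then "To compare behavioral semantic learning performance and errors, behavioral data will be subjected to a one-way ANOVA", with group (TL, DLD) as the only factor. The same account says that after each set of three sentences "the participant will be asked to provide the meaning of the nonsense word, if possible", and that an experimenter "will write down the word provided by the participant".

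Under Participant Information, the answer on how the number of subjects was determined says "the error analysis requires 14 participants/group for power=0.95, f=0.6" and alpha 0.05. For accuracy it gives 16 per group at the same power, effect size and alpha. It names G*Power as the software, sets a target of 25 per group, and claims power of at least 0.8 for all variables at that size.

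**The concern.** Two analyses described as the same test, with the same effect size, power and alpha, cannot need different numbers of children. At least one figure therefore rests on a model or input that the plan does not state, and a reader cannot tell which test was powered.

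The second part is the link between question and test. A one-way ANOVA by group compares one number per child. To say something about types of error, that number must be a type-specific share or index, or the test must be repeated for each type. The supplied text gives no categories, no denominator, no rule for a set left unanswered (although a meaning is requested only where the child can give one) and no rule for several tests. These choices could then be made after the results are known, in the analysis meant to show what kind of semantic deficit the children have.

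**Working it through.** **Sample size**

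Inputs, all from the paragraph on number of subjects: f = 0.6, alpha = 0.05, power = 0.95. The design is two equal groups with a one-way ANOVA (Planned analyses; Research Design and Methods).

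Formula: with n per group, N = 2n. The noncentrality is λ = f² × N = 0.36 × 2n. Power = P(F′(1, N − 2; λ) > F crit), where F crit is the 95th percentile of the central F(1, N − 2).

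| n per group | λ | F crit | power |
|---|---|---|---|
| 14 (stated, errors) | 10.08 | 4.225 | 0.863 |
| 16 (stated, accuracy) | 11.52 | 4.171 | 0.907 |
| 19 | 13.68 | 4.113 | 0.949 |
| 20 | 14.40 | 4.098 | 0.959 |
| 25 (target) | 18.00 | 4.043 | 0.986 |

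The smallest n reaching 0.95 is 20 per group, so neither stated figure is reproduced.

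Attempts to recover them:
- A one-sided t test with d = 2f = 1.2 gives 16 per group (power 0.953). It does not give 14 (0.926), and an F test is non-directional.
- For the stated test, 14 and 16 are the sizes needed for power 0.85 and 0.90.
- For the stated test, power 0.95 at 14 or 16 per group would need f = 0.708 or 0.659.
- The between-groups effect in a repeated-measures run with three measures and correlation 0.5 gives 14. The plan states neither that model nor those two inputs.

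At 25 per group the test keeps power 0.80 down to f of about 0.404, so the claim of at least 0.8 holds for this test at the stated f.

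**What the error score could be**

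1. *Total errors.* If every set not answered correctly is an error, the error rate is 1 minus the proportion correct. A one-way ANOVA on it has the same F and p-value as the accuracy test.

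2. *Each type's share of the child's incorrect responses, tested type by type at 0.05.* Each test is valid alone. Were the tests independent, the chance of at least one false positive would be 1 − 0.95³ = 0.143 for three types and 1 − 0.95⁴ = 0.185 for four. Shares sum to one, so the tests are not independent. Simulation gave the following, with the same error mix in both groups and 25 per group. The assumed ranges were 30 to 100 sets, accuracy 70% in TL and 55% to 70% in DLD, and a between-child SD of 0.3 to 1.0 on the logit scale.

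| types tested | any-type false-positive rate |
|---|---|
| two (one test) | 4.6–5.4% |
| three | 11.3–12.7% |
| four | 16.0–17.9% |

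3. *One pre-specified share or index.* There is one test, at 5%.

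With a Bonferroni adjustment at f = 0.6 and 25 per group, power is 0.957 for three comparisons (alpha 0.05/3) and 0.946 for four (alpha 0.05/4).

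**The case against.** The strongest reply is that nothing in the design depends on the wrong figures. The target is 25 per group, the claim there is only power of at least 0.8, and the stated test has 0.986. That stands: a reader might infer that the study is too small, and the documents do not support it.

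A reader might also infer that the error analysis carries a false-positive rate of 12% to 17%. The documents do not support that either. They give no number of types and do not say that types are tested one by one; two types or a single index would keep the rate at 5%. Nor do they suggest that total errors is the intended score, since the background names types and the sample-size text lists errors apart from accuracy.

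A third tempting inference is that counting silence as an error type would produce false findings. If the groups differ in how often they give no answer, their shares of all incorrect sets truly differ. That is a different quantity, not a false positive. The case there is only for fixing the rule in advance.

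Finally, this is an ethics application form with some pages removed, and it asks for the investigator-developed task to be uploaded. A coding scheme may exist elsewhere, so absence is judged on the supplied text. None of this removes the conflict between 14 and 16, which lies within one paragraph.

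**Conclusion.** The stated figures are wrong as written. For the planned two-group one-way ANOVA at f = 0.6, alpha 0.05 and power 0.95, both analyses need 20 per group, against 14 and 16 stated. This rests only on the documents' own inputs. It is an error in the stated justification and leaves the target of 25 per group sound. The repeated-measures match to 14 is a guess at its origin and carries no weight.

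The undefined error outcome is a real gap of lower rank, mostly missing detail. Its effect on false positives is conditional: about 12% with three separately tested types and about 17% with four, unadjusted. The numbers of types, sets and accuracies behind those rates are assumptions.

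**What to change.** In the paragraph on number of subjects, restate the figure as 20 per group for both accuracy and errors (one comparison, power 0.95), or name the model and inputs that gave 14 and 16. Keep 25 per group.

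Leave the accuracy ANOVA as it is. In Planned analyses and in Research Design and Methods, add for the error analysis:
- The outcome is each error type's share of the child's incorrect responses, not total errors.
- The error categories and the coding of no response are fixed before the data are seen.
- Either one share or index is named as primary, or the tests are adjusted across the types compared.
- The number of children left out is reported by group: those with no incorrect set and, if only answered sets form the denominator, those whose incorrect sets were all unanswered.

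The cost is a written coding scheme and a less favourable stated figure; visits, tasks and target do not change. Naming one primary share or index costs no power through adjustment. Adjusting over several types does, by an amount that depends on the number of comparisons and the no-response rate. In simulations of an assumed shift in mix from 40/35/25 to 25/50/25, Holm adjustment lowered detection of a changed type by up to 16 percentage points with three types and no no-response share. The loss was up to 21 points when a no-response share was added and only answered sets formed the denominator for the types.

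### The accuracy (16 per group) and error (14 per group) sample sizes share one test and one set of inputs; that test needs 20 per group for power 0.95

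*Combined protocol and SAP*

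**What the plan says.** All places are in the combined protocol and SAP.

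- **Test.** Study Abstract, item 4 (Planned analyses): "behavioral data will be subjected to a one-way ANOVA to evaluate a possible effect of group (DLD, TL) on accuracy and the error analysis". The step-by-step description under Research Design and Methods repeats this: "To compare behavioral semantic learning performance and errors, behavioral data will be subjected to a one-way ANOVA to evaluate a possible effect of group". Both places name only two groups, DLD and TL.
- **Sample sizes.** Participant Information, Study Population, answer on how the number of subjects was determined: "the semantic learning accuracy analysis requires 16 participants/group for power=0.95, f=0.6, α =0.05, the error analysis requires 14 participants/group for power=0.95". The text goes on to give the error analysis the same effect size and significance level as accuracy: "the error analysis requires 14 participants/group for power=0.95, f=0.6, α =0.05".
- **Software.** Same answer: "A priori power analyses were conducted with G*Power using preliminary data".
- **Largest stated requirement.** Same answer: "the regression requires 24 participants/group for power=0.95". The target is then set at 25 per group, with a claim of at least 0.8 power for all variables.

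For the two behavioural ANOVAs the plan states no one-sided test, repeated factor, correlation or third group.

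**The concern.** Accuracy and errors have the same planned test, effect size, significance level and power, yet they are given different sizes. At least one figure must therefore be wrong as written, before any calculation is done.

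Two of the five stated sample sizes cannot be reproduced from the analysis described. If the described test is the real one, the 0.95 power claimed for both is too high. If another test was used for sizing, the sample-size text and the analysis text describe different analyses.

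**Working it through.** **Inputs.** Two groups of equal size n, so N = 2n; f = 0.6; α = 0.05; required power 0.95 (Study Population). Test: one-way ANOVA on group (Study Abstract; Research Design and Methods).

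**Formula.** The F statistic has 1 and N − 2 degrees of freedom and noncentrality λ = N·f². Power is the probability that this noncentral F exceeds the central 5% critical value.

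**The plan's figures and the size needed, at f = 0.6**

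| n per group | N | λ = N × 0.36 | Power |
|---|---|---|---|
| 14 (plan, errors) | 28 | 10.08 | 0.863 |
| 16 (plan, accuracy) | 32 | 11.52 | 0.907 |
| 19 | 38 | 13.68 | 0.949 |
| 20 | 40 | 14.40 | 0.959 |
| 25 (target) | 50 | 18.00 | 0.986 |

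Neither 16 nor 14 reaches 0.95. The smallest size that does is 20 per group. For this F test, 16 and 14 are the smallest sizes for power 0.90 and 0.85 respectively.

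**Could f have been rounded to 0.6?** Take f from 0.55 to 0.649.

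| f | Smallest n per group for 0.95 | Power at 16 | Power at 14 |
|---|---|---|---|
| 0.55 | 23 (0.954) | 0.853 | 0.800 |
| 0.60 | 20 (0.959) | 0.907 | 0.863 |
| 0.649 | 17 (0.956) | 0.944 | 0.911 |

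Solving for f instead, power 0.95 needs f = 0.659 at 16 per group and f = 0.708 at 14. Both would round to 0.7, so rounding does not explain the figures.

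**Could other settings have been used?** Some settings the plan does not state give these sizes at f = 0.6. The correlations ρ are assumptions, since the plan gives none. For a repeated-measures between-groups test with m measurements, λ = N·f²·m / (1 + (m − 1)ρ).

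| Setting not in the plan | n per group | Power |
|---|---|---|
| One-sided t-test, d = 2f = 1.2 | 16 | 0.953 |
| One-way ANOVA with three groups | 16 | 0.958 |
| Repeated measures, between groups, m = 2, ρ = 0.6 | 16 | 0.956 |
| Repeated measures, between groups, m = 3, ρ = 0.7 | 16 | 0.956 |
| Repeated measures, between groups, m = 2, ρ = 0.4 | 14 | 0.955 |
| Repeated measures, between groups, m = 3, ρ = 0.5 | 14 | 0.963 |
| Repeated measures, between groups, m = 4, ρ = 0.6 | 14 | 0.955 |

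None of these is the analysis described. The ANOVA F test is non-directional, only two groups are named, and a one-way ANOVA has no repeated factor.

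**Room below the target, per analysis.** At 0.95 power the described test leaves 25 − 20 = 5 children per group (5/25 = 20%). The stated figures imply 25 − 16 = 9 (36%) for accuracy and 25 − 14 = 11 (44%) for errors.

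**The case against.** **Nothing in the design changes.** The operative claim is that 25 per group gives at least 0.8 power. At f = 0.6 the two behavioural analyses have power 0.986 at that size, and 0.968 even at f = 0.55. The disputed sizes themselves exceed 0.80 at f = 0.6. This stands, and it limits the point to reporting.

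**The loss margins are not the plan's own.** The plan states no attrition allowance, and the analyses draw on the same children. The study-wide margin at 0.95 power is set by the regression at 24 per group, which leaves 25 − 24 = 1 child per group whichever behavioural figure is right. This also stands: the figures 5, 9 and 11 hold for each analysis taken alone.

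**The test description may simply be abbreviated.** The central hypothesis predicts poorer outcomes in DLD, which would fit a one-sided test, and 16 is then exactly the minimum (15 gives 0.941). The background speaks of types of errors, which could mean several categories per child. With three measures and an assumed correlation of 0.5, 14 is the minimum (13 gives 0.949). This is a live explanation, but it does not remove the mismatch. No such setting is stated, and each conflicts with the two-group one-way ANOVA written in both analysis passages. It does mean that 20 per group is the right replacement only if that ANOVA is what was intended.

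**Conclusion.** The concern holds. Identical inputs for one named test are given two different sizes, and neither follows from that test. At f = 0.6 and α = 0.05, power is 0.907 at 16 per group and 0.863 at 14, against a stated 0.95; 20 per group are needed. No f that rounds to 0.6 reaches 0.95 at either size.

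This rests on the standard noncentral F calculation with equal groups and on taking the analysis text at its word. The documents establish the mismatch but not which side of it is wrong. The consequence is confined to the reported justification: both analyses remain well powered at the target of 25 per group at the stated effect size.

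**What to change.** 1. For each behavioural analysis, state the G*Power settings used: test family, sidedness, number of groups, number of repeated measures, assumed correlation and unrounded effect size.
2. If the two-group one-way ANOVA is the intended test, replace both figures with one statement: accuracy and errors, each tested by that ANOVA, need 20 children per group for power 0.95 at f = 0.6 and α = 0.05. Alternatively, keep 16 and 14 and give their power as 0.91 and 0.86.
3. If another test was intended, correct the analysis text in Study Abstract item 4 and in Research Design and Methods to match the settings in step 1.
4. Keep the target of 25 per group.

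The cost is wording only, with no extra enrolment. If the ANOVA is retained, the apparent room below the target at 0.95 power shrinks to 5 per group for each of these analyses. If a different test was used, the two analysis passages also need editing.
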